6.1. Study Intervention(s) Administered

All enrolled participants will receive mirikizumab.

Detailed instructions for mirikizumab administration, ccl will be provided separately by the sponsor or designee.

Sites must have resuscitation equipment, emergency medications, and appropriately trained personnel available during the CCI monitoring period.

Administration of mirikizumab should always be done after all other visit assessments are completed, as specified in SoA (see Section 1.3).

Returned study intervention should not be re-dispensed to the participants.

This table provides information about mirikizumab administration in this clinical study.

Intervention Name	Mirikizumab	
Study Period	II	III
Dosage Level(s)	CCI mg CCI	CCI mgCCI
Route of Administration	CCI	via CCI mLCCI
Administration	 onsite by authorized study personnel only maximum rate of 10 mg/min by over no less than 30 min. 	 onsite by authorized study personnel, or via self-administration by participant or caregiver, as indicated in the SoA (Section 1.3)
Participant Monitoring	hour following administration. Note: Longer monitoring is allowed when required by investigator practice or local standard of care	According to investigator practice or local standard of care
Authorized as Defined by EU Clinical Trial Regulation	Not authorized in EU	Not authorized in EU

Abbreviations: EU = European Union; CC SoA = Schedule of Activities;

Packaging and labeling

Study intervention, mirikizumab, will be supplied by the sponsor or its designee in accordance with current Good Manufacturing Practice. Study intervention will be labeled as appropriate for country requirements.

6.1.1. Self-Administration Training

In this protocol, self-administration is defined as the CCI of mg mirikizumab by the participant or caregiver.

Completion of self-administration training is required for eligibility in the Continued Access Period.

It is recommended that self-administration training starts at Visit 6 (Week occur during at least 2 visits and start no later than Visit 8 (Week occur) for participants planning to complete self-administration training. See SoA in Section 1.3.

During self-administration, the site staff should use the Study Drug Administration Training Log to train participants on the completion of the SDAL.

After completion of self-administration training at 2 or more visits, trained participants may self-administer may mirikizumab and complete the SDALs at any remaining dosing visits. At these visits, the site staff should observe the self-administration of mirikizumab and review the completion of the SDAL completion are identified, the site staff should take corrective actions, including retraining as appropriate.

6.2. Preparation, Handling, Storage, and Accountability

The investigator or designee must confirm appropriate storage conditions have been maintained during transit for all study intervention received and any discrepancies are reported and resolved before use of the study intervention.

Only participants enrolled in the study may receive study intervention. Only authorized study personnel may supply, prepare, and administer study intervention. Exception: participants or caregivers may administer mirikizumab injections at dosing visits during or following self-administration training.

All study intervention must be stored in a secure, environmentally controlled, and monitored (manual or automated) area in accordance with the labeled storage conditions with access limited to the investigator and authorized study personnel.

The investigator or authorized study personnel are responsible for study intervention accountability, reconciliation, and record maintenance (that is, receipt, reconciliation, and final disposition records).

Further guidance and information for the final disposition of unused study interventions are provided in the Pharmacy Manual.

6.3. Assignment to Study Intervention

All participants will be centrally assigned to mirikizumab using an interactive web-response system. Before the study is initiated, the log in information and directions for the interactive web-response system will be provided to each site.

6.4. Blinding

This is an open-label study and all participants will receive mirikizumab. There is no blinding.

6.5. Study Intervention Compliance

Period II: cc dosing

mg mirikizumab must be administered under medical supervision by the investigator or designee. The date and time of each dose administered will be recorded in the source documents and will be provided to the sponsor as requested.

Period III: CCI dosing

mg mirikizumab must be administered by authorized study personnel or self-administered by the participant or caregiver, per protocol training procedures. The date and time of each dose administered should be recorded in the source documents and provided to the sponsor as requested.

6.6. Dose Modification

Dose modifications are not permitted in this study.

6.7. Treatment of Overdose

There is no known antidote for mirikizumab.

In the event of an overdose, the investigator should:

- Contact the medical monitor immediately.
- Initiate supportive treatment according to the participant's clinical signs and symptoms.
- Closely monitor the participant for any AE/SAE and laboratory abnormalities (hematology and chemistry), as well as vital signs and oxygen saturation.
- Evaluate the participant to determine, in consultation with the medical monitor, whether study intervention should be interrupted.

6.8. Prior and Concomitant Therapy

Section 10.10 provides the list of permitted medications with dose stabilization guidance.

Section 10.11 provides the list of prohibited medications.

Section 6.8.1 provides corticosteroid taper instructions for participants taking oral corticosteroids.

The medical monitor should be contacted if there are any questions regarding concomitant or prior therapy.

Continued use of nonprescription herbal supplements/medicines that are taken specifically for the treatment of UC should be discussed with the medical monitor.

The medical monitor should be contacted if there are any questions regarding concomitant or prior therapy.

All participants should maintain their usual medication regimens for concomitant conditions or diseases throughout the study, unless those medications are specifically prohibited (Section 10.11).

Stable doses of permitted UC medications, other than oral corticosteroids, should be continued, unless dose modification is required due to AEs, or dose modification is otherwise specified in Section 10.10. Other medications may be allowed if they are approved by the medical monitor.

If a medication is needed to treat an AE or for appropriate medical management, the investigator should base decisions on participant and clinical factors.

Reporting of prior or concomitant therapy

Any medication or vaccine, including over-the-counter or prescription medicines, bowel preparations, vitamins, and herbal supplements; or other specific categories of interest, that the participant is receiving at the time of enrollment or receives during the study must be recorded in the concomitant medication CRF, along with:

- Reason for use
- Dates of administration including start and end dates, and
- Dosage information including dose and frequency for concomitant therapy of special interest.

6.8.1. Corticosteroid Use and Taper

Local administration of corticosteroids, for example, intranasal, inhaled, and intra-articular, is allowed if required for the management of preexisting conditions and AEs.

Periods I and II

For participants who enter the study on corticosteroid therapy, the prescribed dose must have been stable for at least 2 weeks before the screening endoscopy. The prescribed dose should remain stable for the duration Study Periods I and II.

Period III

For participants who enter the Study Period III on corticosteroids, tapering of corticosteroid therapy may be initiated at Visit 6 (Week ...).

The investigator should use clinical judgment of the benefit/risk of steroid tapering for each individual participant as corticosteroids should be tapered as soon as possible following the recommended tapering regimen below or as preferred per local practice.

The recommended tapering schedule for oral corticosteroids (other than budesonide extended-release tablets [budesonide MMX]) is as follows:

- Dose >10 mg/day prednisone or equivalent: taper daily dose by column until receiving 10 mg/day, and then continue tapering at column until 0 mg/day.
- Dose ≤10 mg/day prednisone or equivalent: taper daily dose by CCl until 0 mg/day.

The tapering schedule for oral budesonide MMX (≤9 mg/day) is to CCl of tablets from daily to every other day for CCl of the discontinue.

The recommended tapering schedule for participant receiving oral beclomethasone dipropionate (gastro-resistant prolonged-release tablet) mg/day is to reduce tablets to mg every other day for CCL and then discontinue.

In participants who cannot tolerate the corticosteroid taper without recurrence of clinical symptoms, CCI

are needed, consult the medical monitor.

In situations where the steroid tapering is paused, the tapering regimen (as described above) should be CCI, if possible.

6.8.2. Prohibited Medications

Administration of prohibited medications for the treatment of UC, approved or investigational, constitutes treatment failure. Use of such medications should not be withheld if, in the opinion of the investigator, failure to prescribe them would compromise participant safety. Participants who require a prohibited medication to treat their UC must be discontinued from study intervention, complete an ED visit, and a posttreatment follow-up visit.

A participant who requires a prohibited medication for a non-UC indication should be discussed with the medical monitor.

Section 10.11 provides the list of prohibited medications and details.

6.8.3. Vaccine Administration During the Study

Prohibited vaccines

Use of BCG vaccination is prohibited throughout the duration of the study and for 12 months after discontinuation of study intervention.

Live attenuated vaccines such as measles, mumps, rubella, or varicella are prohibited during the study and for 3 months after the last dose of study intervention. Use of emergency vaccinations (such as rabies or tetanus vaccinations) is allowed with no timing restriction.

Allowed vaccines

Use of non-live (killed, inactivated, subunit, or RNA-based) vaccinations is allowed for all participants; however, their efficacy with concomitant mirikizumab is unknown. If a permitted non-live vaccine is needed, it is recommended that study intervention not be administered on the same day as a vaccination.

7. Discontinuation of Study Intervention and Participant Discontinuation/Withdrawal

Discontinuation of specific sites or of the study as a whole are handled as part of Section 10.1.9.

7.1. Discontinuation of Study Intervention

When necessary, a participant may be permanently discontinued from mirikizumab. If so, the participant will discontinue mirikizumab and will remain in the study to complete procedures for an ED visit, if applicable, and posttreatment follow-up, as shown in the SoA.

A participant should be permanently discontinued from study intervention (mirikizumab) if

the participant becomes pregnant during the study

in the opinion of the investigator, the participant should permanently discontinue the study intervention for safety reasons

the participant has a lack of clinical benefit or disease worsening and

o requires treatment with medication(s) at doses higher than those specified in Sections 10.10 and 10.11.

or

o requires treatment with prohibited medications specified in Section 10.11.

the participant undergoes surgery for active UC

the participant has a systemic hypersensitivity reaction (Section 7.1.3)

the participant has a diagnosis of the following during the study:

- malignancy (except for successfully treated basal or squamous cell skin carcinoma),
 or
- intestinal dysplasia

the participant develops HIV infection.

the participant develops active TB or has untreated LTBI (Section 8.2.7).

HBV or HCV: the participant tests positive for HBV DNA (see Section 8.2.8.1) or tests positive for HCV RNA (Section 8.2.8.2)

Note: The HBV DNA result is to be confirmed if initial test result is positive but below the level of quantification (Section 8.2.8.1).

Prior to discontinuation of any immunomodulatory and/or immunosuppressive therapy due to hepatitis, including study intervention, it is recommended that the participant is to be referred to, evaluated, and managed by a specialist physician with expertise in evaluation and management of viral hepatitis.

The timing of discontinuation from study intervention relative to the initiation of any antiviral treatment for hepatitis is to be based on the recommendation of the consulting specialist physician, in conjunction with the investigator, and aligned with medical guidelines and standard of care.

7.1.1. Suicidal Ideation or Behavior

It is recommended that the participant be assessed by an appropriately trained professional to assist in deciding whether the participant is to be discontinued from study intervention if

- the participant scores a 3 for Item 12 (thoughts of death or suicide) on the CCl at any time in the study, or
- the participant reports suicidal ideation or suicidal behaviors during the study.

A psychiatrist or appropriately trained professional may assist in the decision to discontinue the participant or assist in preparing a safety monitoring plan for the participant should they continue in the study.

7.1.3. Hypersensitivity Reactions

If the investigator determines that a systemic hypersensitivity reaction has occurred related to study intervention administration, the participant may be permanently discontinued from the study intervention, and the sponsor's designated medical monitor should be notified. If the investigator is uncertain about whether a systemic hypersensitivity reaction has occurred and whether discontinuation of study intervention is warranted, the investigator should consult the medical monitor.

7.1.4. Temporary Discontinuation

Temporary withholding of study intervention is required if the participant meets any of the following infection-related criteria during the study.

Criteria for temporary discontinuation of study intervention	Next steps	
Infection-related criteria		
Serious or opportunistic infections, as defined in Section 5.2	Withhold until resolution of all acute clinical signs and symptoms, and completion of all appropriate anti-infective treatment. If participant is diagnosed with LTBI, see Section 8.2.7.	
A participant diagnosed with LTBI during the study	Permanently discontinue from study intervention unless the participant is a candidate for LTBI treatment, and is treated for LTBI as follows: ○ Study intervention is temporarily held for at least the color weeks of LTBI treatment. ○ After receiving at least weeks of appropriate LTBI therapy (as per WHO or US CDC guidelines), if there is no evidence of hepatotoxicity (ALT/AST must remain ≤2 times ULN) or other treatment intolerance, study intervention may be resumed. ○ The participant must complete appropriate LTBI therapy to remain eligible to receive study intervention.	
HBV DNA results that are reported as positive, or as detecting HBV DNA, but HBV DNA is below the level of quantification	Contact medical monitor. Repeat HBV DNA testing as soon as is feasible. If HBV DNA is confirmed as positive, then study intervention must be permanently discontinued.	
 Hematology Laboratory Criteria Platelet count < 50.0 x 10⁹/L WBC <2.0 x 10⁹/L (leukopenia) Absolute Neutrophil Count <1.0 x 109/L (< 1.0 × 103/μL or < 1.0 GI/L) (neutropenia) Lymphocyte count <500 cells/uL (<0.5 x 10³/μL or <0.5 GI/L) (lymphopenia) 	Contact medical monitor. Discuss timing of repeat hematology laboratory panel and term for withholding intervention.	

7.2. Participant Discontinuation/Withdrawal from the Study

Discontinuation is expected to be uncommon.

A participant may withdraw from the study:

- at any time at the participant's own request for any reason or without providing any reason
- at the request of the participant's designee (for example, parents or legal guardian)
- at the discretion of the investigator for safety, behavioral, compliance, or administrative reasons

if enrolled in any other clinical study involving an investigational product, or enrolled in any other type of medical research judged not to be scientifically or medically compatible with this study

if the participant, for any reason, requires treatment with a therapeutic agent that is prohibited by the protocol and has been demonstrated to be effective for treatment of the study indication. In this case, discontinuation from the study occurs prior to introduction of the new agent.

At the time of discontinuing from the study, if possible, the participant should complete procedures for an ED visit and posttreatment follow-up, if applicable, as shown in the SoA (see Section 1.3). If the participant has not already discontinued the study intervention, the participant will be permanently discontinued from the study intervention at the time of the decision to discontinue the study.

If the participant withdraws consent for disclosure of future information, the sponsor may retain and continue to use any data collected before such a withdrawal of consent. If a participant withdraws from the study, the participant may request destruction of any samples taken and not tested, and the investigator must document this in the site study records.

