10.11. Appendix 11: Prohibited Medications

This section outlines medications that are prohibited during the treatment phase of the study and during washout periods prior to the screening endoscopy, if applicable. Use of the medications listed in this appendix is allowed at the discretion of the investigator after a participant discontinues study intervention and completes the ED visit.

Drug Class (examples) –	Screening and Washout	Tre	atment
Comments by Study Period			
	I	II	III
Biologics, JAK inhibitors, Immunomodulators			
Anti-TNF antibodies	DC CCI prior to screening	Pro	hibited
(adalimumab, golimumab, infliximab)	endoscopy		
CCI	DC CC prior to screening	Pro	hibited
	endoscopy. See Section 5.2.		
Anti-integrin antibodies	DC CCI prior to screening	Pro	hibited
(vedolizumab)	endoscopy		
JAK inhibitors, oral	DC cc prior to screening	Pro	hibited
(tofacitinib, upadacitinib)	endoscopy		
CCI	DC CC prior to screening	Pro	hibited
	endoscopy		
Immunomodulators for UC: oral AZA, 6-MP,	Initiation or increase above	the stable dose	at screening is
MTX	-	uring the study	
Immunomodulatory medications, oral or IV:	DC CCI prior to screening	Pro	hibited
cyclosporine, mycophenolate mofetil,	endoscopy		
thalidomide, tacrolimus.			
Other immunomodulatory medications should			
be discussed with medical monitor prior to use			
Corticosteroids			
Rectally administered corticosteroids,	DC CCI prior to screening	Pro	hibited
enemas or suppositories	endoscopy		
Oral corticosteroids for UC	Initiation or increase above the		se at screening is
	 	uring the study	
Oral budesonide standard formulation	DC CCI prior to screening	Pro	hibited
- Note: this is not budesonide MMX	endoscopy		
IV corticosteroids for UC	DC CCI prior to screening		orticosteroids
	endoscopy	•	hibited
Systemic corticosteroids for non-UC indication,	DC CCI prior to screening	Pro	hibited
oral or IV. Allowed exceptions: See Section	endoscopy		
10.10.			

Drug Class (examples) –	Screening and Washout	Treatment			
Comments by Study Period	I	II	III		
Other					
Rectally administered 5-ASA therapies - enemas, suppositories	DC CC prior to screening endoscopy	Pro	hibited		
Agents depleting B or T cells (alemtuzumab, rituximab, visilizumab)	DC col prior to screening endoscopy	Pro	hibited		
Any investigational therapy, biologic or non-biologic	DC or half-lives, whichever is longer, prior to screening endoscopy	Pro	hibited		

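### The protocol contradicts itself on whether a participant whose worsening UC requires a prohibited UC-effective drug stays in the study for follow-up or leaves it before the drug starts

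*Protocol*

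**What the plan says.** Four current sections of the protocol govern this event.

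- **Section 6.8.2** treats a prohibited UC drug as treatment failure. On access it says: "Use of such medications should not be withheld if, in the opinion of the investigator, failure to prescribe them would compromise participant safety". On what follows, the participant "must be discontinued from study intervention, complete an ED visit, and a posttreatment follow-up visit".
- **Section 7.1** lists, as grounds for permanently stopping mirikizumab, lack of benefit or worsening together with a need for a drug prohibited in Section 10.11. In such cases "the participant will discontinue mirikizumab and will remain in the study to complete procedures for an ED visit" (where applicable) and posttreatment follow-up.
- **Section 7.2** covers leaving the study. One listed reason is needing, for whatever cause, a prohibited agent with shown efficacy in UC. It then adds: "In this case, discontinuation from the study occurs prior to introduction of the new agent". On leaving, the ED visit and follow-up are requested where possible and where applicable.
- **Section 10.11 (Appendix 11)** says that the listed drugs are "allowed at the discretion of the investigator after a participant discontinues study intervention and completes the ED visit". It states no exception.

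Two other places matter. The Schedule of Activities (SoA, Section 1.3) makes the ED visit a requirement for everyone who stops mirikizumab before Visit 10, and times Visit 801, a telephone visit, from Visit 10 or the ED visit. Section 8.3.1 ends AE and SAE collection when study participation ends. After that point, an SAE is reported only if the investigator becomes aware of it and deems it possibly related to study treatment or participation.

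**The concern.** The protocol separates stopping treatment (7.1) from leaving the study (7.2), and it puts the same clinical event under both. Two sites could each follow a section of the protocol and end with different study status, different follow-up duties and different safety data for the same kind of participant.

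The main stake is safety collection. These participants have recently been dosed, their disease is worsening and they are about to start another potent drug. If participation ends before that drug starts, routine AE/SAE collection ends there too. A lesser stake is clarity for the site. Section 6.8.2 protects access to the drug on safety grounds, while Appendix 11 makes access follow the ED visit without repeating that protection.

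**Working it through.** The plan has no figure to reproduce here, and no arithmetic applies. The check sets the passages side by side.

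**1. Do 7.1 and 7.2 cover the same event?** The 7.1 trigger is lack of benefit or worsening plus need for a drug listed in 10.11. The 7.2 trigger is need for a prohibited drug that works in UC. Anti-TNF antibodies are prohibited in 10.11, and inclusion criterion 9b names them among therapies approved for UC. A participant with worsening UC who needs one meets both triggers, so the overlap is real.

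**2. What does each section require?**

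| Section | Study status | ED visit and follow-up | When the drug may start |
|---|---|---|---|
| 6.8.2 | Stops study intervention | Mandatory | No order set; not withheld if safety would be compromised |
| 7.1 | Remains in the study | Expected (ED visit where applicable) | Not stated |
| 7.2 | Leaves the study | Where possible and applicable | After leaving the study |
| 10.11 | Stops study intervention | ED visit must be complete | After the ED visit; no exception |

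**3. Can one sequence satisfy all four?** Visit 801 falls after the ED visit. That leaves four possible orders once mirikizumab is stopped:

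- *ED visit, Visit 801, leave the study, drug.* This meets every section only if the drug can wait until Visit 801. No section asks for that wait, and it goes against 6.8.2 if waiting would compromise safety.
- *ED visit, leave the study, drug.* This meets 7.2 and 10.11. It goes against 7.1, because the participant is out before follow-up.
- *ED visit, drug, Visit 801 while in the study.* This meets 6.8.2, 7.1 and 10.11. It goes against 7.2.
- *Drug, ED visit, Visit 801 while in the study.* This meets 6.8.2 and 7.1. It goes against 10.11 and 7.2.

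For any participant who starts the drug before Visit 801, at least one section is breached. The 6.8.2 and 10.11 pair is different: it clashes only when safety would be compromised and the ED visit cannot be done first. None of these orders is put forward here as the right one.

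**4. What is collected after the drug starts?** Applying Section 8.3.1:

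| Event after the new drug starts | Participant still in the study (6.8.2, 7.1) | Participant already out (7.2) |
|---|---|---|
| Non-serious AE | Collected to Visit 801 | Not routinely collected |
| SAE not judged related | Collected to Visit 801 | Not reported |
| SAE judged possibly related | Collected to Visit 801 | Reported if the investigator becomes aware |

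SAP Table AMBZ.4.1 counts everyone who stopped mirikizumab before Visit 10 as entering follow-up. For those outside continued access, it ends that period at the later of the last study visit and the study disposition date. The period therefore takes its length from what the site did, and does not fill the gap.

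**The case against.** The strongest case on the other side has four parts.

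- Section 7.2 is headed as a list of reasons why a participant may withdraw, so it can be read as permissive. It still asks for the ED visit and follow-up, and the SoA makes the ED visit required for everyone who stops early.
- Section 6.8 leaves medication needed for an AE or for appropriate management to the investigator's judgement, and 6.8.2 has its own safety clause. Urgent treatment is therefore addressed.
- No minimum interval is set between the ED visit and the drug, and the SoA as read marks no endoscopy at that visit. Same-day completion would often satisfy both 6.8.2 and 10.11.
- Section 8.3 keeps investigators responsible for following up events that are serious, related or the cause of stopping study intervention, and 8.3.1 keeps a route for possibly related SAEs.

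Much of this stands. Follow-up under 7.2 is weakened, not removed, and the access conflict is confined to cases where the ED visit cannot come first. It does not remove the main point. The sentence in 7.2 about order is not worded as optional, and a duty that 6.8.2 makes mandatory is conditional there. The later SAE route also leaves out non-serious AEs and SAEs not judged related.

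A reader might infer stronger things that the documents do not support:

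- *Three mutually incompatible orders of treatment.* Section 6.8.2 sets no order, and its access clause depends on the investigator's view of safety.
- *A contradiction for non-UC use, because 7.2 applies whatever the cause.* Section 6.8.2 says: "A participant who requires a prohibited medication for a non-UC indication should be discussed with the medical monitor". That discussion can settle whether the participant withdraws, so both can be followed.
- *ED data that cannot be compared between sites, with harm to a planned result.* The visible SAP shows no analysis built on ED assessments, and the missing-data text is redacted.

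**Conclusion.** The contradiction holds in a limited form. For worsening UC that requires a prohibited UC-effective drug, Sections 6.8.2 and 7.1 conflict with 7.2 on study status and on whether the ED visit and follow-up are mandatory or conditional, unless the drug waits until Visit 801. The consequence is possible loss of non-serious AEs and of SAEs not judged related, between study exit and Visit 801, at sites that follow 7.2. The conflict between 10.11 and 6.8.2 is secondary and conditional.

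The size cannot be given as a number. The documents state no rescue rate, Section 7.2 expects discontinuation to be uncommon, and the interval to Visit 801 is redacted. A count of affected participants out of the planned 160 would rest wholly on an assumed rate. It would also count everyone needing such a drug, not only those for whom the sections cannot all be followed. No bias in the primary endpoint is claimed, because the handling of missing data is redacted.

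The conclusion assumes that sites read the sentence on order in 7.2 as an instruction, and that leaving the study means the end of participation in Section 8.3.1. It is a wording fault that should be corrected because it touches safety collection in recently dosed participants.

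**What to change.** The sponsor should reconcile Sections 6.8.2, 7.1, 7.2 and 10.11 into one consistent statement covering sequence, scope (use for UC only, or any use) and study status. Which clinical order applies, and whether the participant leaves the study, are for the sponsor to settle.

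For data collection, the protocol should add that, whichever sequence is kept, AE and SAE collection continues through Visit 801 unless the participant withdraws consent. Section 8.3.1 should say the same. The start date of the new agent should be recorded, so that events can be placed before or after it.

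The cost is protocol wording. Visit 801 already exists as a telephone visit, so no new visit is needed.
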